9.6 Safety Analysis

9.6.1 Adverse Events

AEs will be coded using the most recent version of the Medical Dictionary for Regulatory Activities (MedDRA) and will be grouped by system, organ, and class (SOC) and preferred term (PT) designation. The severity, frequency, and relationship of AEs to investigational product will be presented by SOC and PT groupings. Listings of each individual AE including start date, stop date, severity, relationship to IP, outcome, action taken (including any treatment administered), and duration will be provided.

Every AE will be assessed for whether or not it qualifies as an SAE. All SAEs will be categorized and listed according to the following categories: Congenital Anomaly or Birth Defect; Persistent or Significant Disability/Incapacity; Results in Death; Requires or Prolongs

Hospitalization; Other Medically Important Serious Event; or Life-Threatening. For deaths, the date and cause of death will be collected and listed. For hospitalizations, the dates of admission and release (discharge) will be collected and listed.

Each AE (based on PT) will be counted once only for a given study subject. If the same AE occurred on multiple occasions, the highest severity will be assumed. Thus, study subjects are not counted multiple times in a given numerator in the calculation of frequencies for a specific AE. C-SSRS reports of suicidality or suicidal ideation will be reported as AEs and analyzed as AEs if the investigator determines after an interview with the subject, that the responses are consistent with suicidal ideation or attempt. Tabulation of suicidal ideation by CSSRS will be presented without hypothesis testing; answers to the C-SSRS will be provided in a subject listing.

9.6.2 Clinical Laboratory and Point of Care Tests

For clinical laboratory data, descriptive statistics will be generated for all tests performed at screening and at each clinic visit. If a laboratory analysis is repeated, the last measurement performed prior to the clinic visit will be used in the summary statistics for that clinic visit. If an unscheduled clinical laboratory visit occurs prior to a scheduled visit that is missed due to dropout, then the unscheduled visit will be used in the summary statistics for the missed scheduled clinical visit. If an unscheduled clinical laboratory visit occurs between two scheduled clinical visits, then the data from the unscheduled visit will only be presented in the listings and not in summary statistics. In addition, at each post-randomization clinic visit descriptive statistics for change from baseline will be generated. Laboratory values will be plotted as mean \pm standard error over time. All laboratory measurements will be presented in the listings.

Number and percentage of positive urine drug tests and pregnancy tests for screening visits and all treatment and follow-up visits will be tabulated. Results of all urine drug tests and pregnancy tests will be presented in the listings. The percentage of subjects with a positive urine drug test at any time post start of treatment will also be presented by test type and treatment group.

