In a 12-week randomized-controlled trial comparing twice daily intranasal oxytocin to intranasal placebo (40 IU of oxytocin/dose or placebo three times daily for the first 2 days and then twice daily for the remainder of the 12-week treatment period), Pederson (2017) evaluated treatment effects in patients with AUD who were very heavy drinkers (≥35 standard drinks/week for men, ≥28 standard drinks/week for women). Twelve patients received intranasal oxytocin and 10 patients received placebo of which 13 were males and 9 were females. Statistical analyses revealed that the oxytocin compared to the placebo treatment group had significantly fewer heavy drinking days (P=0.047; about 15 fewer heavy drinking days during the 12-week trial, d=0.97) and drank very significantly fewer drinks/drinking day (P=0.0008; about 2.6 fewer drinks/drinking day during the trial, d=1.83). No significant oxytocin effect on abstinent days was noted. Spielberger state anxiety self-ratings trended weakly toward being lower in the oxytocin compared to the placebo group (P=0.098), corresponding to an on-average 3.5-point difference. There were no group differences in alcohol craving scores. No severe adverse events occurred. Also, vital signs remained stable and laboratory measures remained within normal limits in all subjects except for transient, asymptomatic, and mild hyponatremia in three oxytocin subjects.

In a human laboratory double-blind, crossover study of 32 non-treatment seeking alcohol abusing (defined as per Diagnostic and Statistical Manual of Mental Disorders, 4th Edition criteria), the effects of single dose intranasal oxytocin (40 IU) were evaluated on measures social perceptual ability, cue-induced craving, and approach bias for alcohol and appetitive imagery (Mitchell-2016). Oxytocin significantly improved recognition of easier items on a social perception task. Although there was no main effect of oxytocin on cue-induced craving for alcohol, a subsequent analysis revealed that oxytocin's effect on craving was moderated by

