# 11.4.4. Safety Analyses

AEs will be coded using the most recent version of the Medical Dictionary for Regulatory Activities (MedDRA) and will be grouped by system organ class (SOC) and preferred term (PT) designation. The severity, frequency, and relationship of AEs to investigational product will be presented by SOC and PT groupings. Listings of each individual AE including start date, stop date, severity, relationship, outcome, and duration will be provided. Each AE (based on PT) will be counted once only for a given study subject. If the same AE occurred on multiple occasions, the highest severity will be assumed. Thus, study subjects are not counted multiple times in a given numerator in the calculation of frequencies for a specific AE. C-SSRS reports of suicidality or suicidal ideation will be reported as AEs and analyzed as AEs if the investigator determines after an interview with the subject that the responses are consistent with suicidal ideation or attempt.

Clinical chemistry, urine drug screen results, pregnancy test results, BAC results, and SNAQ scores will be reported as summary statistics for each assessment time point. The percentages of subjects in each group with a SNAQ score ≤14 at each visit will be presented. Vital signs will be presented as summary statistics and change from baseline. The proportions of ECG results considered clinically significant will also be provided. In addition, change from baseline (shift tables) will also be presented for clinical chemistry data. The numbers and percentages of subjects who had urine tests positive for THC at each time point for all subjects, for subjects who were positive at baseline, and who were negative at baseline (representing new use) will be summarized. The numbers and proportion of subjects who reported CIWA-AR scores ≥ 10 at any time after the start of dosing will be presented. Buss-Perry Aggression scores, SNAQ scores and body weight changes will be presented for each visit and will be compared between groups using repeated measures ANOVA. The numbers and proportions of subjects mild, moderate, severe microsomia or any smell loss (anosmia) compared with screening assessment using the UPSIT will also be presented.

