2. INTRODUCTION

This statistical analysis plan (SAP) for Protocol No. NCIG-007R, "Randomized, Double Blind, Placebo-Controlled Trial of the Efficacy of Intranasal Oxytocin for the Treatment of Alcohol Use Disorder" describes and expands upon the analytical plan presented in the protocol.

This document contains all planned analyses, reasons and justifications for these analyses for all study data. This plan also includes sample tables, figures, and listings that will be populated. The SAP will follow the International Conference on Harmonization of Technical Requirements for Registration of Pharmaceuticals for Human Use (ICH) Guidelines as indicated in Topic E3 (Structure and Content of Clinical Study Reports), Topic E8 (General Considerations for Clinical Trials) and Topic E9 (Statistical Principles for Clinical Trials). The structure and content of the SAP provides sufficient detail to meet the requirements identified by the Food and Drug Administration (FDA) and ICH.

The following sources were used in preparation of this SAP:

- Protocol # NCIG-007R, Protocol Version No.: 4.0; Version Date: 05Jul2022
- ICH Guidance Topics E9, E3 and E8

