Table 104: Summary of Other Services Used During Treatment Period

	Placebo	Oxytocin
Services	(N=xx)	(N=xx)
Self Help Meetings		
N	XX	XX
Mean	XX.X	XX.X
SD	XXX.XX	XXX.XX
Median	XX	XX
Min-Max	(xx-xx)	(xx-xx)

	Placebo	Oxytocin
Services	(N=xx)	(N=xx)
Have you visited another health professional to get help reducing drinking?		
N	Xx	XX
Yes n (%)	xx (xx)	xx (xx)

Programmer note: categorize type of professional for those categories reaching 5%

Table 105: Summary of ECG Results

	ASP8062	Placebo
Result	(N=xx)	(N=xx)
Screening		
Normal	nn (xx.x%)	nn (xx.x%)
Abnormal, Not Clinically Significant	nn (xx.x%)	nn (xx.x%)
Abnormal, Clinically Significant	nn (xx.x%)	nn (xx.x%)
End of Study		
Normal	nn (xx.x%)	nn (xx.x%)
Abnormal, Not Clinically Significant	nn (xx.x%)	nn (xx.x%)
Abnormal, Clinically Significant	nn (xx.x%)	nn (xx.x%)

Table 106: Summary of Blood Chemistries

		Placebo				Oxytocin						
Test	N	Mean	SD	Med	Min	Max	N	Mean	SD	Med	Min	Max
Test Name (units)												
Screening												
Week 6												
Change from baseline												
Weeks 8, 10, 13												

Programmers note: table will include creatinine, ALT, AST, total bilirubin, creatinine, sodium, and potassium.

Table 107: Summary of Positive Urine Drug Tests, Pregnancy Test or BAC > 0.000 Any Time During the Study

	Number (% Positive)					
Test	Placebo	Oxytocin				
THC	xx (xx%)	xx (xx%)				
Cocaine	xx (xx%)	xx (xx%)				
Opioids	xx (xx%)	xx (xx%)				
Methamphetamine	xx (xx%)	xx (xx%)				
Amphetamine	xx (xx%)	xx (xx%)				
Benzodiazapines	xx (xx%)	xx (xx%)				
Buprenorphine	xx (xx%)	xx (xx%)				
Methadone	xx (xx%)	xx (xx%)				
Oxycodone	xx (xx%)	xx (xx%)				
MDMA	xx (xx%)	xx (xx%)				
Barbiturates	xx (xx%)	xx (xx%)				
Pregnancy	xx (xx%)	xx (xx%)				
BAC > 0.000	xx (xx%)	xx (xx%)				

Table 108: BPAQ – Each Evaluation During Maintenance Period

			0	xytocin			Placebo						
Study Week	N	Mean	SD	Median	Min	Max	N	Mean	SD	Median	Min	Max	
Physical Aggression													
6	XX	XXX	XXX	XXX	XXX	XXX	XXX	XXX	XXX	XXX	XXX	XXX	
8	XX	XXX	XXX	XXX	XXX	XXX	XXX	XXX	XXX	XXX	XXX	XXX	
10	XX	XXX	XXX	XXX	XXX	XXX	XXX	XXX	XXX	XXX	XXX	XXX	
13	XX	XXX	XXX	XXX	XXX	XXX	XXX	XXX	XXX	XXX	XXX	XXX	
Verbal Aggress	ion												

6	XX	XXX										
8	XX	XXX										
10	XX	XXX										
13	XX	XXX										
Hostility												
6	XX	XXX										
8	XX	XXX										
10	XX	XXX										
13	XX	XXX										
Anger												
6	XX	XXX										
8	XX	XXX										
10	XX	XXX										
13	XX	XXX										

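### The protocol's chemistry shift tables are missing from the SAP, so the laboratory tables can miss transient or off-schedule low sodium, mainly mild values

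*SAP*

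**What the plan says.** - **Protocol 11.4.4** (and the synopsis, under Safety Analyses) states that "change from baseline (shift tables) will also be presented for clinical chemistry data".
- **SAP 2** says of itself: "This document contains all planned analyses".
- **SAP 9.6.2** plans descriptive statistics at each visit, change from baseline, a plot of mean and standard error over time, and listings. It has no shift table. Of the shells in SAP 12, Table 106 is the only laboratory table, with N, mean, SD, median, minimum and maximum by arm and visit; its note reads "table will include creatinine, ALT, AST, total bilirubin, creatinine, sodium, and potassium". The only shell called a shift table is Table 32, on WHO drinking risk. No reason is given for leaving the chemistry shift tables out.
- **Unscheduled values, SAP 9.6.2.** When the draw falls between two scheduled visits, "then the data from the unscheduled visit will only be presented in the listings and not in summary statistics". When it precedes a visit missed through dropout, "then the unscheduled visit will be used in the summary statistics for the missed scheduled clinical visit".
- **Repeats, SAP 9.6.2.** For a repeated analysis, "the last measurement performed prior to the clinic visit will be used in the summary statistics for that clinic visit".
- **Listings, SAP 9.6.2.** "All laboratory measurements will be presented in the listings".
- **Schedule.** In both schedules of assessments, chemistry is at screening and Weeks 6, 8, 10 and 13. Twice-daily dosing starts in Week 3 (Protocol 6.1).

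**The concern.** Protocol 4.3 names hyponatremia, described there as infrequent, among the effects that have led to stopping intranasal oxytocin. Protocol 4.1.6 reports, from the earlier 12-week trial in alcohol use disorder, short-lived and symptomless "mild hyponatremia in three oxytocin subjects", out of 12 treated.

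A risk of this kind appears as a few subjects with low values for a short time. By-visit means and standard errors barely respond to it. The output that would show it is the one the protocol promised, a by-arm cross-tabulation of baseline grade against on-treatment grade. Without it, the laboratory tables have nothing that counts subjects with low sodium at any time after dosing. SAP 9.6.2 and 9.6.5 do use any-time counts for positive urine drug tests and for CIWA-AR of 10 or more, so this would not be a new kind of summary for the plan.

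**Working it through.** The plan states no figure for laboratory capture, so there is none to reproduce. The check follows a low sodium value through the planned output, then gives the scale.

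**1. Where a low sodium value appears**

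| Value | Table 106 | AE tables | Listing |
|---|---|---|---|
| Below 130, at a scheduled visit | Yes, at least as the visit minimum | Should appear | Yes |
| Below 130, between visits | No, unless it replaces a visit missed through dropout | Should appear | Yes |
| 130 to the lower limit of normal, scheduled | Within the mean and SD; as the minimum only if it is the lowest | Depends on which AE wording is applied | Yes |
| 130 to the lower limit of normal, between visits | No, with the same exception | Depends on which AE wording is applied | Yes |

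The AE column rests on these provisions:
- Protocol Appendix B, Table 6: sodium below 130 down to 120 mmol/L is Grade 3; 130 to the lower limit of normal is Grade 1; there is no Grade 2.
- Protocol 10.2.4: Grade 3 or higher sodium is clinically significant, and an abnormal result is an AE unless it was already abnormal at baseline and has not risen a grade.
- Exclusion criterion 18 bars sodium below 132. No subject eligible on screening sodium starts below 130, so any fall below 130 is a grade increase.
- Protocol 10.2.1 and 10.7 tie laboratory AEs to clinical significance; 10.7 leaves that to the investigator. For Grade 1 values this is narrower than 10.2.4.
- Even under 10.2.4, a subject who enters at 132 and falls to 130 stays in Grade 1 and need not generate an AE. This assumes a local lower limit of normal above 132; the documents give none.

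**2. Expected number of subjects, illustration only**

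Earlier trial: 3/12 = 25%, exact 95% CI 5.5% to 57.2%. Safety uses the Full Analysis Set (SAP 4.0), about 50 per arm. 0.25 × 50 = 12.5, so 12 to 13 subjects. At the interval limits, 0.055 × 50 = 2.75 and 0.572 × 50 = 28.6, so about 3 to 29.

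**3. Effect on a visit mean**

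One subject at 126 mmol/L (the value cited in Protocol 4.1.8) among 50 otherwise at an assumed 140: (140 − 126)/50 = 0.28 mmol/L. Drawn between visits, it contributes nothing to Table 106 unless the dropout exception applies.

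**4. Chance that an episode misses every scheduled draw**

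Assume onset uniform over the 84 days from day 1 to day 85, with draws on days 36, 50, 64 and 85 (the first days of Weeks 6, 8, 10 and 13). An episode of L days is sampled if it starts within the L days before a draw. For L up to 14 these windows do not overlap, so the chance of missing all four draws is 1 − 4L/84.

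- L = 3: 1 − 12/84 = 86%
- L = 7: 1 − 28/84 = 67%
- L = 14: 1 − 56/84 = 33%

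Such an episode is seen only if an unscheduled sample is taken, and that value is then listed only, unless it is recorded as an AE or stands in for a visit missed through dropout.

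**The case against.** A reader might infer that low sodium can vanish from the safety tables altogether. The documents do not support that. A value such as 126 mmol/L is Grade 3, is clinically significant under Protocol 10.2.4 and should be an AE whenever it was drawn. SAP 9.6.1 counts each event at its highest severity, and Tables 95 to 97 show maximum severity by arm for the whole study, Weeks 1 and 2, and Weeks 3 to 12. For hyponatremia recorded as an AE, that is already a by-arm severity table. Table 106 also shows minima, so a very low scheduled value is visible even though the mean hardly moves.

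A reader might also infer that the repeat rule replaces a low value with a later normal one. That is not established. The rule takes the last measurement before the clinic visit. A verification repeat under Protocol 10.7 would normally follow the scheduled draw. On a natural reading it is then an unscheduled value, and the low result stays in Table 106. The rule is ambiguous rather than clearly harmful.

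Keeping off-schedule draws out of by-visit means is ordinary practice, and I do not ask for that to change. The prior evidence is also mixed: the three cases were mild, and Protocol 4.1.9 cites two studies of 12 to 13 weeks with no adverse effect on blood chemistry or electrolytes.

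Two things remain. The shift tables were promised and are absent without explanation. For Grade 1 sodium, the AE route depends on which of three protocol provisions a site follows. A minimum is one number per arm and visit and does not count subjects, and the AE tables do not show baseline grade against worst grade.

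**Conclusion.** The point holds as a mismatch between protocol and SAP with a limited safety consequence. The protocol's chemistry shift tables have no counterpart in the SAP, and the laboratory tables that remain can miss transient or off-schedule low sodium, mainly Grade 1 values. Sodium below 130 mmol/L should still reach the AE tables if Protocol 10.2.4 is followed.

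The size is uncertain. The 12 to 13 of 50 rests on carrying over a rate from 12 subjects with a very wide interval. The 0.28 mmol/L rests on an assumed mean of 140, and the miss probabilities on uniform onset and assumed draw days. The conclusion depends on none of these; it follows from comparing the two documents. A restored table can show only values that were actually drawn.

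**What to change.** In SAP 9.6.2 and the shells, restore the shift table by arm: baseline grade to worst post-dose grade for each analyte, using all scheduled, repeat and unscheduled post-dose values. Keep the by-visit summaries as they are, and state how a repeat is assigned to a visit, including one drawn after it.

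Before grading, reconcile two matters in the protocol:
- the CTCAE version, which is 5.0 in Sections 10.2.5 and 10.7 and 4.03 in Appendix B;
- the wording on when a laboratory value becomes an AE, in Sections 10.2.1, 10.2.4 and 10.7.

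The cost is one added table from data already collected and listed, plus settling the grading version and AE wording. The sampling schedule and treatment rules are unaffected.

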9.6.3 Vital Signs, Weight, and ECG

Vital signs will be presented as summary statistics and change from baseline. The percentage of ECG results considered abnormal and clinically significant will be provided. Body weight will be presented as summary statistics and change from screening. No statistical tests will be performed. Vital signs, ECG results, and weight measurements for all visits will be presented in the listings.

9.6.4 Blood Alcohol Concentration

The number and percent of subjects at any clinic visit that have a BAC > 0 will be tabulated. All BAC measurements will be presented in the listings.

9.6.5 CIWA-AR Scores

The number and percentage of subjects who reported CIWA-AR scores ≥ 10 at any time after the start of dosing will be presented. Fisher's exact test will be performed. No modeling or imputation will be performed.

9.6.6 Buss-Perry Aggression Questionnaire (BPAQ)

The short form version of the BPAQ is used in this study and is a 12-item self-report measure aggression. Each item is assessed on a 5-point Likert scale assessing the degree to which agreesion-related statements are characteristic of the subject during the past week. The BPAQ includes four subscales: physical aggression (4 items), verbal aggression (3 items), anger (2 items), and hostility (3 items) (Diamond and Magaletta, 2006). Scores for each subscale, which are the sum of the items, will be assessed individually. There is no total score for this scale.

Because the BPAQ is a repeated continuous measure, the BPAQ subscales wil be analyzed using the mixed effects described in Section 9.4.2. Descriptive statistics will be presented for each assessment by treatment group. No imputation will be performed.

9.6.7 Simplified Nutritional Appetite Questionnaire (SNAQ)

The 8-item Council on Nutrition appetite questionnaire scale and its 4-item derivative The Simplified Nutritional Appetite Questionnaire (SNAQ) were developed to assess appetite and predict weight loss. The changes in appetite during the study will be evaluated using the clinically simpler version of the two scales, the SNAQ (Wilson 2005). The 4 item SNAQ asks: 1) My appetite is; 2) When I eat; 3: Food tastes; and 4) Normally I eat; with 5 possible responses that are scored numerically from 1 to 5. The sum of the responses is the total scale score. A SNAQ score ≤14 indicates significant risk of at least 5% weight loss within six months. The number and percentages of subjects in each group with a SNAQ score ≤14 at each visit will be summarized. Fisher's exact test will be used at each visit. No imputation for missing data will be performed. A mixed effects analysis on the continuous SNAQ score, as described in Section 9.4.2, will be used to evaluate change over time. No imputation will be performed.

9.6.8 University of Pennsylvania Smell Identification Test (UPSIT)

The UPSIT will be assessed at screening and other clinic visits throughout the study to determine if intranasal investigational products cause any changes in sensory discrimination. It consists of 4 booklets each containing 10 microencapsulated (scratch and sniff) odors. The UPSIT test has been studied in individuals with alcohol addiction and has shown that this population generally had generally lower UPSIT scores that non-drinking controls. Outcomes will be captured in Adverse Event tables.

9.7 Drug Exposure and Retention

Medication compliance, defined as the amount of investigational product taken as a proportion of the total amount prescribed per protocol, will be evaluated for the oxytocin and placebo groups based on the Subject Diary. Average IU per day of investigational product taken based on the the vial weight difference prior to and after dispensment will also be reported overall and weekly will be reported for the oxytocin and placebo groups. Exposure and compliance averages will be compared across treatment groups using t-tests at each week and overall. If the data are meaningfully skewed then the Wilcoxon rank-sum test will be used. The same test will be used for each week and overall. The research participation rate, defined as percentage of subjects with complete drinking data, will be compared between treatment groups. A Fisher's Exact test will

be used for the overall participation rate, weekly tests will not be performed. In addition, the percentage of subjects discontinuing medication or early withdrawal from the study and a listing of these reasons for discontinuation will be provided. No statistical inference will be performed for reasons of discontinuation.

